5. TREATMENT OF SUBJECTS

5.1 Investigational product/treatment

In this study, all 60 participants will undertake an 8-week intervention with either a prebiotics supplement (arm 1 and 3) or a placebo supplement (arm 2 and 4), which will be consumed once per day (1 sachet in the morning) during the first week, and twice per day (1 sachet in the morning and 1 sachet in the evening) for the remainder of the intervention. During the entire trial, research subjects will maintain their normal routines concerning their diet, medication use, and exercise pattern.

Prebiotics supplement: Prebiotics preparation is composed of three individual fibers (40% acacia gum, 20% partially hydrolyzed guar gum, and 40% resistant starch) from Winclove Probiotics B.V. (Amsterdam, the Netherlands).

Placebo (control): Placebo preparation is composed of food-grade corn starch and maltodextrin from Winclove Probiotics B.V. (Amsterdam, the Netherlands).

5.2 Use of co-intervention (if applicable)

Not applicable.

5.3 Escape medication

Not applicable.

6. INVESTIGATIONAL PRODUCT

6.1 Name and description of investigational product(s)

Prebiotics: acacia gum (AG), partially hydrolyzed guar gum (PHGG), and resistant starch (RS).

- Acacia gum (AG) also known as gum arabic, is obtained from the stems and branches of *Acacia senegal* and *Acacia seyal* trees. AG is a nonviscous, soluble, highly branched fiber, and its main components are arabinose and galactose [36]. It is a safe, natural, and plant-based food additive used for many centuries. For further details see product brochure (D6).
- Partially hydrolyzed guar gum (PHGG) is a soluble fiber produced by controlled partial enzymatic hydrolysis of GG which is derived from guar seeds, and it consists of galactomannan, which is characterized by high viscosity. In the modern food industry, GG is used as a food additive in various food products for thickener, emulsion stabilizer and as fiber source [37, 38]. For further details see product brochure (D6).
- Resistant starch (RS) refers to the fraction of starch which is not hydrolyzed in the small intestine, but is fermented by bacteria in the colon. It exists in many common foods, including legumes, cereals, grains and vegetables (especially potatoes) [39]. For further details see product brochure (D6).

The prebiotics preparation is composed of three non-digestible carbohydrates (40% acacia gum, 20% partially hydrolyzed guar gum, and 40% resistant starch). In total 3 grams of prebiotic preparation contains 1.2 grams acacia gum, 0.6 gram partially hydrolyzed guar gum, and 1.2 grams of resistant starch.

The prebiotics, consisting of a mix of non-digestible fermentable fibers described above has been selected on the basis of (1) Total butyrate production, (2) Gradual fermentation throughout the entire colon (instead of fast fermentation in the proximal colon), (3) A good prebiotic tolerability index (low gas production), and (4) Commercial considerations.

Placebo: corn starch and maltodextrin.

Corn starch and maltodextrin are digestible carbohydrates, that are completely digested and absorbed in the proximal small intestine, and thus do not reach the colon, which makes them suitable placebo dietary compounds and the reason why they are widely used in dietary intervention studies.

The placebo consists of two digestible carbohydrates (20% maltodextrin and 80% corn starch). In total 3 grams of placebo preparation contains 0.6 gram of maltodextrin and 2.4 grams of corn starch). A Technical Data Sheet has been provided for both prebiotic as well as placebo product. For further details see product brochure (D6).

All ingredients are non-pathogenic, non-toxigenic and are classified as Generally Recognized As Safe (GRAS) as food ingredients. The prebiotics and placebo supplements are produced by WinClove Probiotics B.V., Amsterdam, the Netherlands. WinClove is a National Sanitation Foundation (NSF) International Certified Good Manufacturing Practice (GMP) Facility for manufacturing dietary supplements. WinClove's food safety management system is International Organization for Standardization (ISO) 22000:2005 certified for the development and production of pre- and probiotics.

6.2 Summary of findings from non-clinical studies

Prebiotics: acacia gum (AG), partially hydrolyzed guar gum (PHGG) and resistant starch (RS).

In vitro and animal models have been employed to study AG, PHGG or RS, with regard to their potential beneficial effect on health.

- Using an *in vitro* colon model inoculated with healthy human fecal material, AG showed the potential prebiotic effects, as it promoted the SCFAs production, especially butyrate [40].
- In a mice colitis model, rectal administration of AG (30 mg/kg) showed significant effects in reducing the inflammatory markers, and the stronger therapeutic effect were observed when combining with anti-inflammatory drug 5-Aminosalicylate (5ASA) [41].
- In a mice colitis model, PHGG and RS boosted SCFAs and butyrate production in the colon. In addition, they reduced intestinal inflammation [42] and induced proliferation of butyrate producing bacteria [43].

As described earlier in sections 1 and 3, we have tested the mix of AG, PHGG and RS using *in vitro* fecal batch fermentation models. In this study, four prebiotics candidates were incubated with fresh stool samples from UC patients in remission or from UC patients with mild active disease over a 48 hour period. The prebiotic (acacia gum, partially hydrolyzed guar gum, and resistant starch), that is selected for this PREDUCTOME study showed the most promising effects, namely (unpublished results);

- Increased production of butyrate and other SCFAs
- Promotion of the growth of butyrate producing bacteria
- Higher prebiotics tolerance defined as stimulated SCFAs production while minimal gas production

Collectively, these pre-clinical data show that the selected prebiotics could potentially have a beneficial effect on the course of UC by modulating butyrate production.

6.3 Summary of findings from clinical studies

Prebiotics: acacia gum (AG), partially hydrolyzed guar gum (PHGG), and resistant starch (RS).

Many clinical studies with the supplementation of AG, PHGG, or RS have been performed to investigate prebiotics effects (e.g., modulating the gut microbiome and boosting butyrate production) and GI tolerance.

- AG is slowly fermented compared with other fermentable fibers [44], therefore it is well-tolerated, i.e., less GI symptoms after consumption. Cherbut et al found AG did not induce adverse GI effects even when consumed up to a daily dose of 30 grams in healthy subjects [45]. A study by Marzorati et al also observed that blending AG with fructo-oligosaccharides (FOS, a well-researched prebiotic) can help to extend the time of fermentation of FOS in the colon [46].
- Partially hydrolyzed guar gum (PHGG) showed no side effects when consumed in 20-40 grams per day [47]. Besides of favouring butyrate-producing bacteria [48], PHGG also benefits bowel function. Increased stool frequency in constipated individuals and improved stool consistency and abdominal pain have previously been reported [49, 50].
- In general, in healthy adults, doses of RS up to 30 grams per day are well tolerated [51]. A dose-response study indicated that a daily dose of 20-50 grams of RS supplementation for one week resulted in beneficial changes in fecal microbiota and fecal metabolites in healthy individuals [52].

6.4 Summary of known and potential risks and benefits

No serious adverse events are expected from the administration of the prebiotics/placebo. If adverse effects occur, they are likely to relate to minor GI symptoms, such as bloating or flatulence or a minor change in defecation, especially when one uses prebiotics for the first time [53]. In our case, UC patients are already used to GI complaints, hence they are expected to report less bloating and flatulence. These effects are expected to disappear within a few days.

Furthermore, to minimize GI complaints due to a sudden intake of the prebiotics/placebo supplement, there will be a gradual increase in dosage: only 1 sachet will be consumed per day in the first week of the intervention period, followed by 2 sachets per day for the remainder of the intervention.

Nevertheless, in case of suspected serious adverse events, the coordinating investigator will immediately notify the Ethics Committee, all study personnel and the manufacturer of the product about the nature of the event. A decision on continuation or discontinuation of the trial will be made by the coordinating investigator in agreement with the Ethics Committee. All the adverse events also will be noted in the Case Report Forms.

6.5 Description and justification of route of administration and dosage

The boxes of prebiotics/placebo will be given to subjects by the coordinating investigator. Boxes include prebiotics/placebo sachets and Winclove's user instruction. Subjects

should consume prebiotics/placebo twice a day in the morning before breakfast and in the evening before dinner during the 8-week intervention period. Prebiotics/placebo will be administered orally. The content of the sachet needs to be dissolved in a glass of water or juice and should be stirred before consumption. The sachets need to be stored at room temperature in their original package.

6.6 Dosages, dosage modifications and method of administration

3 grams of prebiotics per time, twice a day for 8 weeks.

3 grams of placebo per time, twice a day for 8 weeks.

Prebiotics and placebo and powders are similar in colour, solubility, and taste.

The dose of non-digestible fermentable fibers has been selected to maximize the potential benefits but to limit potential GI side effects and is based on previous studies that have been conducted.

6.7 Preparation and labelling of Investigational Product

Preparation and labelling will be conducted at Winclove Probiotics B.V. All components are legally admitted as food additives or food components. Winclove is a NSF International Certified GMP Facility for manufacturing dietary supplements. Winclove works with the food safety management system ISO 22000:2005 and is certified for the development and production of pre- and probiotics.

After block randomization, the sachets will be labelled with: study name, instruction for use, expiration date and storing conditions. For further details see the product label in product brochure (D6). The products will be dispensed by the coordinating investigator.

6.8 Investigational Product accountability

The boxes of prebiotics/placebo will be given to subjects by the coordinating investigator (and are supplied to the subjects for the entire study period). Boxes include sachets and Winclove's user instruction. The shipment with boxes and sachets will be delivered to Laboratory of Microbiology, Wageningen University & Research, Wageningen by courier. The food supplements will be safely stored and locked by key at the Laboratory of Microbiology and only accessible by the research team (a list of the randomization codes is provided, which can only be opened in case of emergency). The product will be kept at room temperature. The coordinating investigator will distribute the boxes to participants in person. For compliance reasons, the patients will be asked to save all the empty sachets, and return everything (used and unused sachets) to the coordinating investigator after the end of the intervention. After counting the empty sachets, to get numbers on protocol compliance, all study material can be destroyed. As this is a food supplement, there is no need for special waste treatment.

7. NON-INVESTIGATIONAL PRODUCT

Not applicable.

8. METHODS

8.1 Study parameters/endpoints

8.1.1 Main study parameter/endpoint

Response (mean P-SCCAI score) between arms at T = 8 weeks:

At T = 8 weeks (the end of the intervention), the P-SCCAI score will be collected via the P-SCCAI questionnaire. As main endpoint, the mean P-SCCAI score for each arm will be determined and compared to each other to determine the difference in response at T = 8 weeks.

P-SCCAI is derived from the original SCCAI questionnaire by translating into patients' comprehensible language, and has been validated to give substantial agreement with the original SCCAI [54]. P-SCCAI refers to disease symptoms during the previous week. It contains 13 items clustered into six domains: bowel frequency (during the day), bowel frequency (during the night), urgency of defecation, blood in stool, general well-being, and a number of defined extracolonic features of UC (i.e. arthritis, erythema nodosum, pyoderma angrenosum, uveitis).

8.1.2 Secondary study parameters/endpoints

Response over time

In addition to week 8, subjects need to fill out the P-SCCAI questionnaire at T = 0, 4, 12, and 60 weeks to determine the response over time. Comparisons will be made between groups as well as within subjects over time. With P-SCCAI score <= 2 being regarded as clinical remission, and a decrease in the P-SCCAI score by more than two points from baseline being regarded as clinical response [30, 31, 55] (see F1). We will also determine whether subjects have reached clinical remission and/or showed a clinical response over time.

Mucosal inflammation

At T= 0, 8, 12, and 60 weeks, a fecal sample will be provided by subjects for calprotectin measurement.

GI complaints: (e.g. abdominal pain, bloating, flatulence)

At T= 0, 4, and 8 weeks, the GI complaints will be assessed by the GSRS questionnaire. The GSRS contains 15 items clustered into five domains (reflux, abdominal pain, indigestion, diarrhea and constipation) addressing different gastrointestinal symptoms [56]. It has a seven-point graded scale where 1 represents the absence of troublesome symptoms and 7 represents very

troublesome symptoms (see F1). The reliability and validity of the GSRS are well-documented, and norm values for a general population are available [57].

Stool consistency and frequency

At T = 0, 4, and 8 weeks, subjects will be asked to keep diaries to record stool frequency (bowel movement per day) and consistency of each stool using Bristol stool form scale (see F1) on a daily basis for 7 days.

Gut microbiota and SCFAs: (e.g. microbiota composition, SCFAs profile)

At T = 0, 8, 12, and 60 weeks, a fecal sample will be provided by subjects for 16S rRNA gene-based microbiota profiling and SCFAs measurement. Subsequent analyses of a variety of microbial ecological characteristics, including microbiota composition, α -diversity (diversity within the sample), β -diversity (diversity between the samples), population dynamics over time, and group differences will also be conducted.

Health-related quality of life

At T = 0, 4, and 8 weeks, health-related quality of life will be assessed by the SIBDQ questionnaire (see F1). SIBDQ is a 10 item shortened version of the original IBDQ which was 32 items. It has a seven-point graded scale where 1 represents very troublesome symptoms and 7 represents the absence of troublesome symptoms. Measures quality of life as measured in four domains (bowel symptoms, emotional health, systemic systems and social function) [58]. Its reliability and responsiveness to change has been validated in UC [59].

Medication use

At T= 0, 4, 8, 12 and 60 weeks, information of medication use will be extracted from patient record and diary. It consists of the current medication use (e.g., aminosalicylates, corticosteroids, immunosuppressive agents, antimicrobial agents, and inhibitors of tumour necrosis factor-alpha (TNF- α)). Medication changes at week 4, 8, 12, and 60 provide information on disease development, with a downgrade means improvement and an upgrade means worsening of UC.

Safety parameters

At T= 0, 4, and 8 weeks, safety parameters (i.e., incidence of adverse events) will be monitored by patient record and diary. In this diary, all relapse-relevant information, including the need for systemic steroids, hospitalization, and surgery will be collected.

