Intervention: An 8-week intervention period with four parallel arms: 1) predicted responders with prebiotics treatment (acacia gum, partially hydrolyzed guar gum, and resistant starch), 2) predicted responders with placebo (maltodextrin and corn starch), 3) predicted non-responders with prebiotics treatment, 4) predicted non-responders with placebo, during which the study participants consume the respective supplement (3 grams, twice daily).

Main study parameters/endpoints: The main parameter is the response (mean P-SCCAI score) between arms at T = 8 weeks. The secondary parameters are the response over time at T = 0, 4, 8, 12, and 60 weeks, mucosal inflammation (fecal calprotectin), gastro-intestinal (GI) complaints, stool consistency, stool frequency, fecal microbiota composition, fecal short-chain fatty acids concentrations, health-related quality of life, medication use, and safety parameters.

Nature and extent of the burden and risks associated with participation, benefit and group relatedness: This study has a relatively low burden for the participants. They have to

consume the commercially available supplement twice daily for eight weeks. Besides, several questionnaires (one long FFQ questionnaire on one occasion, two short ones on five occasions, five short ones on three occasions) have to be completed, which is all possible from home. On five occasions they will collect fecal samples (which will be collected from their homes by us). There are no physical risks for the study participants, although some participants may experience minor bloating complaints at the start of using the prebiotics.

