3. STUDY DESIGN

This study is a double-blind randomized placebo-controlled parallel trial. A summary of the study set-up and workflow is shown in **Figure 3**.

[figure not shown]

Figure 3 PREDUCTOME study: set-up and workflow

The study consists of the screening, intervention, and the follow-up periods.

During the **screening** period, approximately one hundred and seventy-seven UC patients will be recruited. P-SCCAII score data will be collected to select mild UC patients which is defined as 3-5 points on a 19-point scale. A stool sample will also be provided by patients to determine the Bacteroidetes level by quantitative polymerase chain reaction (qPCR) quantification of the number of total bacteria and Bacteroidetes. Based on the baseline microbiota from a subject in a fecal microbiota transplantation trial [20], in which healthy donors, sustained responding UC patients, and non-responding UC patients had an average relative abundance of 8%, 5%, and 19% Bacteroidetes, respectively, predicted responders are defined as UC patients having with a relative abundance of Bacteroidetes <=10% in their feces, while predicted non-responders are defined as UC patients with a relative abundance of Bacteroidetes >=15% in their feces. A total of sixty screened mild UC patients will continue with this study that consists of thirty predicted responders and thirty predicted non-responders.

To assess the habitual dietary intake of the last month, a validated food frequency questionnaire (FFQ, see F1) will be taken at the baseline. The data will also be used for potential correlation analysis with other parameters as diet is considered an important modulator of the intestinal microbiota. For the intervention, at **baseline**, selected participants

need to fill out several questionnaires including P-SCCAI (once), gastrointestinal symptom rating scale (GSRS, once), stool consistency (Bristol stool scale, daily for 7 consecutive days), stool frequency (daily for 7 consecutive days), short inflammatory bowel disease questionnaire (SIBDQ, once). Information of medication use and adverse events will be extracted from patient record and diary. In addition, they have to collect a stool sample for determining calprotectin level, microbiota composition, and SCFAs profile.

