4.2 Inclusion criteria

1. Male and female subjects aged 18 to 65 years*
2. Body Mass Index (BMI) between 18 and 30 kg/m² (self-reported)
3. Ulcerative Colitis confirmed via previous endoscopy and histology
4. Mild active UC as defined by P-SCCAI score of 3 to 5 (range 0 to 19)
5. Frequent relapse (at least one exacerbation in the last two years)
6. No known allergy to any components of the study product (self-reported)
7. Signed informed consent
8. Stable UC medication defined as no switch to other medication or no dose change
9. Mobile phone on which apps (used for questionnaires) can be downloaded (iOS version 9 and newer, Android version 4.4 and newer. Phones manufactured after 2013 are usually suitable)
10. Stable dietary pattern during the study

* We only include adults (age 18-65) as previous studies have shown that adolescent and elderly microbiota as well as UC presentation in adolescents can be different from adults[32, 33].

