4.4 Sample size calculation

The primary objective of the trial is to validate the prediction that a higher response (lower mean P-SCCAI score) is induced at T= 8 weeks by the prebiotics intervention in mild UC patients with low Bacteroidetes levels (predicted responders), but not in those with high Bacteroidetes levels (predicted non-responders) in their gut. Mild UC is defined as a P-SCCAI score of 3 to 5. According to an extensive study regarding UC disease activity conducted in the Netherlands, mild UC patients have a P-SCCAI score of 3.5 ± 0.5 (Mean \pm standard deviation (SD)), and patients in remission score at 1.0 ± 0.33 (Mean \pm SD)[34, 35].

In a series of germinated barley foodstuff (GBF) intervention studies, 10 mild to moderately active UC patients received 30 grams of GBF (equals to 10 grams fiber) daily for 4 weeks [4], and researchers found a significant decrease in clinical activity index scores. In a later study, another group of 11 mildly to moderately active UC patients consuming 20-30 grams of GBF (equals to 6.66-10 g fiber) daily for 4 weeks showed similar results, with decreases in clinical activity index scores [28].

Based on two-sided statistical testing for unpaired continuous data, an $\alpha=0.05$ (chance on type-I error) and $\beta=0.10$ (chance on type-II error), and assuming a 20% difference of mean P-SCCAI score between predicted responders with prebiotics and predicted non-responders with prebiotics, it was calculated that at least 11 subjects per group are needed for the primary outcome P-SCCAI ($\mu_1=3.5$; $SD_1=0.5$; $\mu_2=2.8$). According to previous trials on prebiotics on IBD patients, a 20% of drop-out rate is commonly seen. Given that the intervention duration is 8 weeks long, followed by a 1 year follow-up, higher dropout rate (30%) is expected. To compensate for a 30% drop-out rate, 15 subjects per group are needed.

To reach inclusion of 30 predicted responders and 30 predicted non-responders, we made an estimate how many subjects we need to screen based on the earlier obtained microbial composition of stool samples from UC patients in the Ede area. Around 50% of these subjects were categorized as low Bacteroidetes subjects (predicted responders) and while 17% of them as high Bacteroidetes subjects (predicted non-responders). To include these responders we will need to screen 177 mild UC patients.

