8.3 Study procedures

A detailed description of procedures is shown in **Table 1**.

Table 1 Procedures

Page 1 of 1

Informed consent procedure

Informed consent procedure
One or more information meetings will be organized prior to the study. In this meeting, the investigators will explain the background, objectives and study procedures. During this meeting, there will be time for the potential research subjects to ask questions.

After the information event, subjects have two weeks to decide whether they are interested in participation or not. Research subjects who are willing to participate will receive the informed consent and the screening package which includes the P-SCCAI questionnaire and one stool collection kit. Then within one week, subjects will receive packages with corresponding products and instructions.

If COVID-19 restrictions are still in place, we would also provide the option of having online information meetings via Microsoft Teams (“Teams is designed and developed in compliance with the Microsoft Trustworthy Computing Security Development Lifecycle (SDL), <https://docs.microsoft.com/en-us/microsoftteams/teams-security-guide>”). No personal data will be collected or send via this route. If preferred, research subjects will always have the option to attend a physical meeting.

Screening

Subjects who fulfil all inclusion criteria and none of the exclusion criteria will be invited to a screening.

One stool sample will also be provided via the specific stool collectors (**Figure 4**). For female participants, pee gutters will also be provided to accurately separate stool from urine. After collection, stool material will be immediately frozen at the home freezers of the subjects, transported on dry ice (via courier) to the laboratory and subsequently frozen at -80 °C until further

Figure 4 Stool collector analysis. DNA will be isolated from part of the stool samples and subsequently be used for qPCR. Primers

targeting total bacteria and Bacteroidetes will be used to quantify the total gene copies and calculate the relative abundance of Bacteroidetes in the stool. Subjects that have a relative abundance of Bacteroidetes $\leq 10\%$ will be assigned to the predicted responders group, while those who have a relative abundance of Bacteroidetes $\geq 15\%$ will be assigned to the predicted non-responders group.

Baseline

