At baseline, selected participants need to fill out several questionnaires P-SCCAI, FFQ [60], GSRS [61], Bristol stool form scale [62], stool frequency, SIBDQ [58], information of medication use and adverse events will be extracted from patient record and diary. All questionnaires can be found in F1 Questionnaires. The GSRS questionnaire provides baseline GI complaints and tolerance information. P-SCCAI provides disease activity information. FFQ provides information regarding the usual foods consumed and the frequency of consumption. Bristol stool form scale provides stool consistency information. SIBDQ provides information on health-related quality of life.

One stool sample will also be provided. The sample will undergo the same collection and storage procedures as those in the screening period. DNA will be isolated from part of the stool samples and subsequently be used for 16S rRNA gene-based microbiota profiling using NG-Tax [63]. The stool sample will be also used for measurements of fecal calprotectin using enzyme-linked immunosorbent assay (ELISA) methods [64], and SCFAs concentrations using high-performance liquid chromatography (HPLC) [65].

Dietary intervention period (8 weeks)

During the intervention period, the subjects will consume the respective supplement (3 grams/sachet) twice per day. To minimize potential GI complaints that might occur due to intake of the prebiotics/placebo supplement, there will be a gradual increase in dosage that only 1 sachet daily will be consumed in the first week of the intervention period, followed by 2 sachets daily for the remainder of the intervention. The patients will be asked to save all the empty sachets.

At T= 4, and 8 weeks, subjects will also need to complete short questionnaires on response (P-SCCAI, once a week), GI complaints and tolerance (GSRS, once a week), stool frequency and consistency (Bristol stool form scale, a 7-day record at each week), SIBDQ (once a week). Information of medication use and adverse events will be extracted from patient record and diary (once a week).

At the end of the intervention period (T= 8 weeks), the participants will provide a second stool sample for fecal calprotectin measurements, 16S rRNA gene-based microbiota profiling, and SCFAs profile analysis. We will determine response with P-SCCAI score.

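### Clinical remission is an absolute P-SCCAI of 2 or less with no condition on the T=0 score, so a patient who has drifted to 2 or less before the first sachet and stays there counts as a remitter at weeks 4 to 60

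*Protocol*

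**What the plan says.** **Entry.** Inclusion criterion 4 (section 4.2) reads "Mild active UC as defined by P-SCCAI score of 3 to 5 (range 0 to 19", with no time point. Section 3 places the check in the screening period, where "score data will be collected to select mild UC patients which is defined as 3-5 points on a 19-point scale". Section 8.3 says that consenting patients receive "the screening package which includes the P-SCCAI questionnaire and one stool collection kit".

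**T=0.** The score is taken again later: "At baseline, selected participants need to fill out several questionnaires P-SCCAI" (section 8.3, Baseline). No range is attached to this second score, and the running text does not say what happens if it is 2 or less. The two occasions are distinct. The Summary says "On five occasions they will collect fecal samples", and five collections are obtained only by counting screening and T=0 separately, with weeks 8, 12 and 60 as the other three.

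**Outcome.** Section 8.1.2 sets the definitions: "With P-SCCAI score <= 2 being regarded as clinical remission, and a decrease in the P-SCCAI score by more than two points from baseline", the second part being clinical response. Section 10.2 repeats them and applies them per subject over T = 0, 4, 8, 12 and 60 weeks. Neither section makes remission conditional on the T=0 score.

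**The concern.** The lowest eligible score is 3 and remission begins at 2. Section 4.4 expects "mild UC patients have a P-SCCAI score of 3.5" on average, so many patients should enter at 3 or 4. For a patient screened at 3, a one-point change between screening and T=0 is enough to meet the remission definition before any product is taken. The score covers only the preceding week, so some movement between two completions is to be expected.

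If that patient is again at 2 or less at week 8, the rule records a remission that the treatment did not induce. The same patient cannot be a responder: a fall of more than two points from 2 or less would need a negative score. One unchanged patient is then a remitter and a non-responder at once.

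At stake is the meaning of the secondary remission rate. It would mix remission reached on treatment with remission already present, in every arm, and so make a real prebiotic effect harder to see.

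**Working it through.** **The plan's own figures.** The remission endpoint has no stated sample size or expected rate. The one related figure, 11 per group for the mean score, reproduces: 2 × [0.5 × (1.960 + 1.282) / 0.7]² = 10.7, rounded up to 11. This point does not affect it.

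**Step 1: how many could be at 2 or less at T=0.** The protocol gives no within-patient variability, so it has to be assumed. Take the T=0 score as the screening score plus a normal change with mean 0 and SD s, rounded to a whole number. Then P(T=0 score ≤ 2) = Φ((2.5 − screening score)/s).

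| Screening score | s = 0.5 | s = 1.0 | s = 1.5 |
|---|---|---|---|
| 3 | 15.9% | 30.9% | 36.9% |
| 4 | 0.1% | 6.7% | 15.9% |
| 5 | 0.0% | 0.6% | 4.8% |

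Averaged over the mix of screening scores:

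| Mix | s = 0.5 | s = 1.0 | s = 1.5 |
|---|---|---|---|
| 3 and 4 equally (mean 3.5, SD 0.5, as in section 4.4) | 8.0% | 18.8% | 26.4% |
| 3, 4 and 5 equally | 5.3% | 12.7% | 19.2% |

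The first row is about 5, 11 or 16 of 60 patients, the second about 3, 8 or 12. A mix of 60/30/10 for scores 3, 4 and 5 gives 9.6%, 20.6% and 27.4%, close to the first row.

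**Step 2: how many would be miscounted at week 8.** A patient low at T=0 is miscounted only if also low later. Scores at T=0 and week 8 were simulated with no treatment effect, screening scores 3 and 4 in equal shares, and a correlation of 0 or 0.5 between the two deviations from the screening score.

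| | s = 0.5 | s = 1.0 | s = 1.5 |
|---|---|---|---|
| Week-8 remission, all patients | 8% | 19% | 26% |
| Week-8 remission, patients above 2 at T=0 | 5-7% | 12-17% | 17-25% |
| Share of week-8 remitters already at ≤ 2 at T=0 | 16-39% | 26-49% | 31-52% |

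The patients at 2 or less at both times are the week-8 remitters minus those who were above 2 at T=0. With s = 0.5 this is 8.0 − 6.7 = 1.3% to 8.0 − 4.9 = 3.1%. With s = 1.0 it is 18.7 − 13.8 = 4.9% to 18.8 − 9.7 = 9.1%. With s = 1.5 it is 26.5 − 18.4 = 8.1% to 26.4 − 12.7 = 13.7%. Of 60 patients that is about 1-2, 3-5 and 5-8.

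**Step 3: dilution within a stratum.** For illustration, assume true remission of 40% on prebiotics and 10% on placebo among patients active at T=0, and a fraction q in each arm already in remission who stay there. The observed rates are q + (1 − q) × 0.40 and q + (1 − q) × 0.10, so the difference is (1 − q) × 0.30. Power is for two proportions, 15 per arm, two-sided 5%, normal approximation with pooled variance under the null.

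| q | Rates | Difference | Power |
|---|---|---|---|
| 0 | 40% vs 10% | 30 points | 47% |
| 0.1 | 46% vs 19% | 27 points | 35% |
| 0.2 | 52% vs 28% | 24 points | 26% |

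With q = 0.2 and only the 0.8 × 15 = 12 patients per arm who were active at T=0, the contrast returns to 40% vs 10% and power is 39%. Restricting the denominator costs patients but gives back more than it takes in this example.

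**The case against.** The strongest reply has four parts.

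- **A T=0 check may exist.** The inclusion criterion carries no time point, and Table 1 is not readable in the available text. A re-check shown only there cannot be excluded. This stands as a limit on the finding; the running text contains none.
- **The gap may be short.** Sections 8.3 and 11.2 say product packages follow within one week, which argues for small changes. The start of that week is loosely worded and no maximum interval from screening score to T=0 is given, so this favours the lower end of the range without closing the question.
- **The harm is limited.** Remission is part of a secondary parameter, and section 10.2 names no specific test of remission proportions. T=0 scores are collected, so the problem would be visible to anyone who looked. Randomisation spreads such patients over prebiotics and placebo within a stratum, so the effect there is dilution, not bias towards prebiotics. All of this stands.
- **The wording may already mean new remission.** Section 10.2 speaks of subjects having reached remission, which suggests a change of state. That is probably the intent, but the cut-off as written does not impose it. The denominator could be left to an analysis plan; however, the protocol itself fixes the definition, and fixes it without a baseline condition.

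A reader might also infer more than the documents support:

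- *Every patient low at T=0 is later counted as a remitter.* No: the later score must also be 2 or less, and a chance dip may reverse.
- *Patients are randomised before the T=0 score is taken.* The order is not stated.
- *The primary endpoint is damaged.* The mean score at week 8 does not use the cut-off. A patient at 2 still has room to improve on the protocol's own figures, since remission patients average 1.0 and the planned difference is 0.7.

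**Conclusion.** The point holds as a defect in the definition of a secondary endpoint. On the running text, a patient at 2 or less at T=0 and again at week 4, 8, 12 or 60 is counted as a remitter without any change on treatment, and is excluded by arithmetic from ever being a responder.

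The consequence is an inflated remission rate in all arms and a diluted prebiotics-placebo contrast within each Bacteroidetes stratum. Predicted responders and predicted non-responders are not randomised against each other, so the remission comparison between them could also be biased if T=0 scores differ between the strata.

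The size is not known from the documents. Under an assumed change SD of 0.5 to 1.5 points, with mean 0, about 5% to 26% would be at 2 or less at T=0 for the two main mixes of screening scores. The number miscounted at week 8 is smaller: about 1 to 8 of 60 when screening scores are split between 3 and 4. No claim is made about the primary endpoint.

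**What to change.** In sections 8.1.2 and 10.2, define clinical remission at weeks 4, 8, 12 and 60 as a P-SCCAI score of 2 or less among patients whose T=0 score was 3 or more. Report by arm how many patients were at 2 or less at T=0.

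This uses scores that are already collected and costs only wording, plus a slightly smaller denominator for this secondary endpoint.

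Repeating the 3-5 eligibility check at T=0 is not part of this fix. It would lose patients from the high-Bacteroidetes stratum, which section 4.4 puts at 17% of those typed and which already drives the screening target (30 / 0.17 = 176.5, hence 177).
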